## KEY POINTS

- Conservative feeding therapies are thought to modify GERD symptoms and its consequences. However, in this randomized controlled trial in convalescing neonatal ICU infants with GERD symptoms, when controlling for preterm or full-term birth and severity of esophageal acid reflux index, the effectiveness of acid suppression plus a feeding modification bundle (volume restriction, intra- and post- prandial body positions, and prolonged feeding periods) vs. acid suppression alone, administered over a 4-week period was not superior in improving symptom scores or feeding outcomes.
- Restrictive feeding strategies are of no impact in modifying GERD symptoms or clinically meaningful outcomes. Further studies are needed to define true GERD and to identify effective therapies in modifying pathophysiology and outcomes.
- The improvement in symptoms and feeding outcomes over time irrespective of feeding modifications may suggest a maturational effect. This study justifies the use of placebo controlled randomized clinical trial among NICU infants with objectively defined GERD.

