short- and long-term clinical outcomes among infants treated concurrently over 4 weeks with PPI with randomly assigned feeding strategy modifications while controlling for gestational maturity (pre-term or full-term at birth) and severity of esophageal ARI (3-7%, >7%). Our *hypothesis* was that the study approach (acid suppression, modified feeding volume, duration, and position) was superior in achieving independent oral feeding or a 6-point reduction in I-GERQ-R vs the conventional (acid suppression alone) feeding approach.

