to randomization would have resulted in all patients being treated based on subjective, non-specific symptoms alone. Owing to the strict inclusion and exclusion criteria of this RCT, those with indeterminate and abnormal ARI were treated with a PPI. In the future, a careful RCT that tests the utility of PPI treatment for confirmed acid-GERD by allocating patients to either limited PPI treatment or placebo is indicated to determine whether PPI treatment is needed. The effectiveness of our short-term use of PPI for 4 weeks to improve GERD-attributable symptoms should be tested in future trials. Effect of esophageal acid exposure and therapies on primary mechanistic outcomes of esophageal motility and symptom causation will be addressed in future reports. 5) In routine clinical practice, feeding volumes are modified and alterations in feeding positions are used to manage symptoms. Our study did not show any differences in the outcomes with feeding- and position modifications. Furthermore, volume restriction had no influence on the study outcomes. The improvement in symptoms and feeding outcomes over time irrespective of PPI or feeding modifications may suggest a maturational effect.

It is important to note that major mechanisms of GER, i.e. transient LES relaxation is the major reason for any reflux events- both acid or non-acid substrate. Our therapeutic target was acid reflux index in this study via PPI, feeding volumes, and positional changes. Given that acid GER can also have weakly or non-acid either before or after PPI therapy, and that there were no differences in outcomes between the two groups, we speculate that neither PPI, feeding volume, or positional changes modify the studied indices or symptoms. Maturation under optimal conditions of good nutrition along with placebo-controlled trials are needed to answer the importance of weakly acid or non-acid GER, which would require a multicenter trial with a large group of infants with appropriate physiologic diagnostic testing.

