## **CONCLUSION**

We addressed the current practice controversies in this clinical trial: 1) Screening and identifying acid-GERD objectively is possible in symptomatic infants prior to any pharmacotherapy. 2) Feeding strategy modification (fluid restriction, positional changes, prolonged feeding duration) has no role in decreasing reflux-type symptoms or in improving the primary outcome of achieving independent oral feeds and/or a six-point decrease in I-GERQ-R score. 3) No difference in the prevalence of chronic lung disease was noted between the groups. 4) I-GERQ-R scores decreased across time regardless of treatment group allocations that strongly

support maturational effect. However, we did not detect an effect on *a priori* short-term or long-term outcomes following randomized allocations. As restrictive feeding strategies do not make a difference, placebo-controlled clinical trials in a larger cohort of convalescing NICU infants with objectively determined newer GERD criteria must be addressed in future trials.

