**Table 2. Primary and Secondary Clinical Outcomes and Compliance Measures**

Primary Outcome (intent-to-treat analysis)	Overall (N = 76)	Conventional (N = 36)	Study (N = 40)	P-value
A priori clinical outcome Success, n (%)	29 (38)	16 (44)	13 (33)	0.28
Secondary Outcomes	Overall (N = 72)	Conventional (N = 35)	Study (N = 37)	P-value
I-GERQ-R decrease by 6 – n (%)	24/65 (37)	11/31 (35)	13/34 (38)	0.82
Feeding Outcome at Time 2 – n (%)				0.26
PO	51 (71)	27 (77)	24 (65)	
Transition (PO + Tube)	18 (25)	8 (23)	10 (27)	
Tube	3 (4)	0 (0)	3 (8)	
Length of hospital stay – days	108 [82 - 128]	108 [83 - 125]	98 [81 - 132]	0.89
Hospital stay Inception to Discharge – days	25 [11 - 45]	23 [3 - 39]	27 [16 - 47]	0.26
Weight Growth Velocity (GV) – g/day	27.1 (9.4)	26.5 (7.2)	27.6 (11.1)	0.64
Length GV – cm/day*	0.1 (0.1)	0.1 (0.1)	0.1 (0.1)	0.88
Head Circumference GV – cm/day*	0.1 [0.0 - 0.1]	0.1 [0.0 - 0.1]	0.1 [0.0 - 0.1]	0.87
Feeding Method at Discharge – n (%)				0.32
PO	54 (75)	29 (83)	25 (68)	
Transition (PO + Tube)	14 (19)	5 (14)	9 (24)	
Tube	4 (6)	1 (3)	3 (8)	
Oxygen Requirement at discharge – n (%)	16 (22)	9 (26)	7 (19)	0.49
Compliance to Feeding Methods				
Total Fluid Volume (TFV)				
TFV at Inception- #	N/A	150 [147, 152]	150 [149, 156]	0.8
TFV at Time 2- #	N/A	143 [134, 148]*	133 [126, 137]*	<0.001
# days TFV ≤ 140 / kg / day	N/A	10 [2, 26]	22 [11, 31]	0.005
TFV compliance (TFV <140/kg/d for >75% of time)	N/A	9 (26)	27 (73)	<0.001
Position				
Feeding Position, RSL, %	N/A	5 [1, 17]	78 [12, 94]	<0.001
Feeding in RSL >75% of the time, %	N/A	0 (0)	21 (57)	<0.001
Supine Position Post-Prandial, %	N/A	50 [40, 66]	87 [74, 96]	<0.001
Supine Position Post-prandial >75% of the time, %	N/A	7/34 (21)	27/36 (75)	<0.001
Feeding Duration				
% time feed duration >30 min, %	N/A	4 [0, 37]	15 [0, 69]	0.15
Feeding Duration at Inception, min	N/A	23 [17, 41]	30 [19, 34]	0.64
Feeding Duration at Time 2, min	N/A	23 [18, 28]	26 [20, 30]	0.15
Long-term Follow-up†				
Feeding Method at 6 months – n (%)				0.65
PO	36/50 (72)	21/27 (78)	15/23 (65)	
Transition (PO + Tube)	10/50 (20)	4/27 (15)	6/23 (26)	
Tube	4/50 (8)	2/27 (7)	2/23 (9)	
Feeding Method at 1 year – n (%)				0.11
PO	37/44 (84)	20/22 (91)	17/22 (77)	
Transition (PO + Tube)	4/44 (9)	0/22 (0)	4/22 (18)	
Tube	3/44 (7)	2/22 (9)	1/22 (5)	
CCABSID-III				
Cognitive Score <80 – n (%)	9/44 (21)	5/23 (22)	4/21 (19)	1.00
Cognitive Score – #	95 [90 - 105]	100 [90 - 105]	90 [90 - 100]	0.11

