- Sample Size Determination:
  - From the more recent preliminary data analysis, 83.3% (20/24, 95% CI: 62.6%-95.2%) of patients had success based on symptoms and feeding methods in the innovative strategy group, while only 35% (7/20, 95% CI: 15.4%-59.2%) had success in the standard therapy group. In order to provide greater assurance than afforded by comparing to historical control of the standard therapy, a total of evaluable 100 patients will be randomized into the innovative feeding strategy or standard therapy group. The chi- square test yields 80% power to detect 27% or higher increase in proportion of success while maintaining an overall one-sided  $\alpha$  level of 0.025. This conservative power calculation is supported by the preliminary data and assumes the proportion of success for the standard therapy is around 40% and a group-sequential design with O’Brien-Fleming error spending function.
- Interim Analysis:

- One interim futility analysis will be undertaken at about 50% information prior to the final analysis at 100% information, corresponding to 50 and 100 evaluable patients, respectively. The boundary is determined using Lan-DeMets spending functions to simulate O'Brien-Fleming boundaries with an overall one-sided  $\alpha$  level of 0.025. Using the target proportion of success, the boundary at the futility analysis expressed as a p-value is 0.297. We plan to enroll 120 patients to allow for 20% of attrition.
- Intention to treat analysis:

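### The Conclusion, Key Points and Discussion assert that the feeding bundle has no effect, but the reported counts support only that superiority was not shown

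*Combined protocol and SAP*

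**What the plan says.** Three places in the manuscript part state absence of effect:

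- **Conclusion:** feeding modification "has no role in decreasing reflux-type symptoms" or in improving the primary outcome. The closing sentence treats it as settled that restrictive feeding makes no difference.
- **Key Points:** "Restrictive feeding strategies are of no impact in modifying GERD symptoms or clinically meaningful outcomes".
- **Discussion:** "volume restriction had no influence on the study outcomes".

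The design was a superiority trial. The Introduction's hypothesis is that the study approach "was superior in achieving independent oral feeding or a 6-point reduction in I-GERQ-R". Protocol section 3.3 plans 100 evaluable infants for "80% power to detect 27% or higher increase in proportion of success" at one-sided alpha 0.025, and "assumes the proportion of success for the standard therapy is around 40" per cent. Neither the protocol nor the Statistical Methods section sets an equivalence or non-inferiority margin.

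The trial ended with 76 infants randomised (36 conventional, 40 study). The results give p=0.28 for the primary outcome and, in the Table 2 row "I-GERQ-R decrease by 6", 11/31 against 13/34 with p=0.82. The Study Outcomes text gives a confidence interval for each arm. No interval for a difference appears.

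**The concern.** A non-significant superiority test does not show that an effect is absent. That needs an interval narrow enough to exclude every difference that would matter, and a statement of what would matter. Neither is given.

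At stake is what a reader takes from the trial. A clinician who reads the Conclusion or Key Points alone will think the question of symptoms is closed. The claim about volume goes further still: volume restriction was randomised only as part of a bundle, so its separate influence was never tested by randomisation.

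**Working it through.** **Inputs.** Primary composite, intention to treat (Table 2): study 13/40, conventional 16/36. Fall of at least 6 points in I-GERQ-R (Table 2): 13/34 and 11/31. Full oral feeding at Time 2 (Table 2): 24/37 and 27/35. Design (section 3.3): 40% rising to 67%, 50 per arm, one-sided alpha 0.025.

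**Step 1. Reproduce the stated figures.**
- Power with unpooled variance: 0.27 / sqrt[(0.40×0.60 + 0.67×0.33)/50] = 2.81; 2.81 - 1.96 = 0.85, giving 80.3%. Pooled variance gives 78.1%. The stated 80% is reproduced.
- The uncorrected chi-square test gives p=0.284 (primary) and p=0.818 (symptom response), matching 0.28 and 0.82.
- Exact (Clopper-Pearson) intervals match the published arm intervals, for example 19-49% and 28-62% for the primary outcome.

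**Step 2. Intervals for the difference, study minus conventional.** The two-sided 95% interval matches a one-sided 0.025 test. Wald: d ± 1.96 × sqrt[p1(1-p1)/n1 + p2(1-p2)/n2].
- Primary: 0.325 - 0.444 = -0.119; SE = sqrt(0.00548 + 0.00686) = 0.111; **-33.7 to +9.8 points** (Newcombe -32.2 to +9.5).
- Symptom response, observed cases: 0.382 - 0.355 = +0.028; SE = sqrt(0.00695 + 0.00738) = 0.120; **-20.7 to +26.2** (Agresti-Caffo -20.3 to +25.4; score -20.4 to +25.4; Newcombe -19.9 to +24.8).
- Symptom response with the 6 study and 5 conventional infants without a score counted as failures: 13/40 - 11/36 = +0.019; SE = 0.107; **-19.0 to +22.9** (Newcombe -18.5 to +21.9).
- Full oral feeding: 0.649 - 0.771 = -0.123; **-33.0 to +8.5**.

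**Step 3. Power at the size reached.** For 40% against 67% with 36 and 40 infants, power is about 66% (pooled) or 69% (unpooled).

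**Step 4. Check the primary counts against Table 3.** Under the definition in Outcome Measures and protocol section 4.0, success is full oral feeding or the symptom fall for infants not yet on full oral feeds, and both for those already on full oral feeds.
- Tube-fed at inception: oral feeding 11 and 7, symptom fall 7 and 8, both 4 and 2 (conventional and study). Either: 11+7-4 = 14 and 7+8-2 = 13, as the table reports.
- Orally fed at inception, both conditions: 4 and 5.
- Totals: 14+4 = 18 conventional and 13+5 = 18 study, against 16 and 13 in Table 2.

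Table 3 covers 35 and 37 infants. Adding the other 1 and 3 as failures gives 18/36 and 18/40: difference -5.0 points; SE = sqrt(0.00694 + 0.00619) = 0.115; Wald **-27.5 to +17.5**.

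**The case against.** The strongest reply is that calibrated wording is already there. The Abstract, the first Key Point and the Discussion say the bundle was not superior, and the Conclusion adds that no effect was detected. The limitations disclose the shortfall from 100 infants and say the futility rule would have been met at 72. A superiority trial also needs no equivalence margin. All of this is true. It shows that the right wording was available, but the absolute sentences remain in the places most often read. Futility concerns the chance of showing superiority; it does not establish that there is no effect.

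A second reply is that the symptom claim does not rest on one comparison. The Study Outcomes section also reports a positive I-GERQ-R at Time 2 in 13/34 study and 9/31 conventional infants (p=0.43), numerically against the bundle. That interval is equally wide: 0.382 - 0.290 = +0.092; SE = sqrt(0.00695 + 0.00665) = 0.117; -13.6 to +32.1 points.

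Two stronger readings are tempting and should be resisted.
- A reader might infer that the symptom interval nearly reaches the benefit the trial was built to detect. The 27 points were set for the composite, and no document sets a target for symptom response alone. The closeness also depends on the method and analysis set: the upper limit is 26.2 by Wald on observed cases, but about 22 to 23 with missing scores as failures.
- A reader might infer that symptoms are the weakest part of the claim. The developmental comparisons rest on fewer infants. Expressive communication below 80 is 4/11 against 7/14, with a Wald interval 77 points wide (3.92 × sqrt[0.0210 + 0.0179]). The symptom interval is 47 points wide and the primary interval 44.

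**Conclusion.** The point holds as one about the strength of the conclusions. The data support the statement that superiority was not shown. They do not support statements of no role, no impact or no influence.

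On the reported primary counts, a composite gain above about 10 points is excluded at the 95% level, and with it the 27-point design effect. Smaller gains, or a loss of up to about 34 points, are not excluded. If the Table 3 counts are right, the limits move to about -27 and +17; the 27-point gain is still excluded. For symptom response, differences of about 20 points or more in either direction remain possible on the observed cases.

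This does not show that the bundle works or that it harms: every interval above includes zero.

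The figures assume that the Table 2 counts are right, that an unstratified comparison is acceptable (as in the reported chi-square test), and that the Table 3 rows align as the sums in step 4 indicate.

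**What to change.** 1. Reconcile the primary counts (16/36 and 13/40) with Table 3 before publishing any interval for the primary outcome.
2. Report the risk difference with a 95% interval for the primary outcome and for each component, naming the interval method and the analysis set.
3. Replace the absolute statements in the Conclusion (including its closing sentence), Key Points and Discussion with wording such as: superiority of the bundle was not shown; on the reported counts a composite gain above about 10 points, and so the 27-point design effect, is excluded, but smaller gains or a loss of up to about 34 points are not; for symptom response, differences of about 20 points or more in either direction cannot be ruled out on the observed cases. Update these limits if step 1 changes the counts.
4. Do not use the 27-point effect as the benchmark for symptom response.

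The cost is a check of the counts, three intervals and some rewording. No new data are needed. The price is a less firm claim.

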**Table 1. Baseline Demographic and Clinical Characteristics of Enrolled Participants**

Variable	Overall Subjects (N = 76)	Conventional Group (N = 36)	Study Group (N = 40)
At Birth			
Gender, Female – n (%)	37 (49)	18 (50)	19 (48)
Race – n (%)			
African American	11 (15)	3 (8)	8 (20)
Asian	1 (1)	0 (0)	1 (3)
Other	6 (8)	2 (6)	4 (10)
Unknown	1 (1)	1 (3)	0 (0)
White	57 (75)	30 (83)	27 (68)
Ethnicity – n (%)			
Hispanic or Latino	2 (3)	2 (6)	0 (0)
Non Hispanic or Latino	71 (93)	32 (89)	39 (98)
Unknown	3 (4)	2 (6)	1 (3)
Gestational Age (GA) – wks	29.3 [27 - 32.9]	29.3 [28 - 32.2]	29.2 [27 - 33.1]
Preterm birth – n (%)	68 (90)	34 (94)	34 (85)
Birth Weight – kg	1.23 [0.9 - 1.9]	1.2 [0.9 - 1.9]	1.3 [0.9 - 2.1]
Size for Gestational Age – n (%)			
Small (< 10th %)	9 (12)	5 (14)	4 (10)
Average (10th - 90th %)	58 (76)	26 (72)	32 (80)
Large (> 90th %)	9 (12)	5 (14)	4 (10)
Cesarean Delivery – n (%)	50 (66)	22 (61)	28 (70)
At Inception			
Postmenstrual age – wks	41.1 (2.5)	41.3 (2.2)	40.9 (2.7)
Chronologic age – wks	10.9 (4.3)	11.1 (4.5)	10.7 (4.3)
Weight – kg	3.5 (0.8)	3.5 (0.8)	3.5 (0.8)
O 2 Requirement at 36 wks PMA – n (%)	36 (47)	17 (47)	19 (48)
O 2 Requirement at 28 days age – n (%)	46 (61)	21 (58)	25 (63)
Feeding Method – n (%)			
Gavage	2 (3)	0 (0)	2 (5)
Transitional	37 (49)	18 (50)	19 (48)
Oral	37 (49)	18 (50)	19 (48)
Nasal Cannula Oxygen – n (%)	23 (30)	11 (31)	12 (30)
Total Intake Volume – mL/kg/day	150 [149 - 154]	150 [148 - 152]	150 [150 - 157]
Total Oral Intake Volume – mL/kg/day	112 [45 - 150]	112 [57 - 150]	112 [22 - 148]
Acid Reflux Index (ARI) – %	9.3 [6.0 - 17.1]	10 [6.0 - 16.7]	9.1 [5.0 - 17.6]
ARI Category – n (%)			
Indeterminate (ARI 3 - 7%)	26 (34)	12 (33)	14 (35)
Abnormal (ARI > 7%)	50 (66)	24 (67)	26 (65)

Data presented as n (%), Median [IQR], or Mean (SD).

**Table 2. Primary and Secondary Clinical Outcomes and Compliance Measures**

Primary Outcome (intent-to-treat analysis)	Overall (N = 76)	Conventional (N = 36)	Study (N = 40)	P-value
A priori clinical outcome Success, n (%)	29 (38)	16 (44)	13 (33)	0.28
Secondary Outcomes	Overall (N = 72)	Conventional (N = 35)	Study (N = 37)	P-value
I-GERQ-R decrease by 6 – n (%)	24/65 (37)	11/31 (35)	13/34 (38)	0.82
Feeding Outcome at Time 2 – n (%)				0.26
PO	51 (71)	27 (77)	24 (65)	
Transition (PO + Tube)	18 (25)	8 (23)	10 (27)	
Tube	3 (4)	0 (0)	3 (8)	
Length of hospital stay – days	108 [82 - 128]	108 [83 - 125]	98 [81 - 132]	0.89
Hospital stay Inception to Discharge – days	25 [11 - 45]	23 [3 - 39]	27 [16 - 47]	0.26
Weight Growth Velocity (GV) – g/day	27.1 (9.4)	26.5 (7.2)	27.6 (11.1)	0.64
Length GV – cm/day*	0.1 (0.1)	0.1 (0.1)	0.1 (0.1)	0.88
Head Circumference GV – cm/day*	0.1 [0.0 - 0.1]	0.1 [0.0 - 0.1]	0.1 [0.0 - 0.1]	0.87
Feeding Method at Discharge – n (%)				0.32
PO	54 (75)	29 (83)	25 (68)	
Transition (PO + Tube)	14 (19)	5 (14)	9 (24)	
Tube	4 (6)	1 (3)	3 (8)	
Oxygen Requirement at discharge – n (%)	16 (22)	9 (26)	7 (19)	0.49
Compliance to Feeding Methods				
Total Fluid Volume (TFV)				
TFV at Inception- #	N/A	150 [147, 152]	150 [149, 156]	0.8
TFV at Time 2- #	N/A	143 [134, 148]*	133 [126, 137]*	<0.001
# days TFV ≤ 140 / kg / day	N/A	10 [2, 26]	22 [11, 31]	0.005
TFV compliance (TFV <140/kg/d for >75% of time)	N/A	9 (26)	27 (73)	<0.001
Position				
Feeding Position, RSL, %	N/A	5 [1, 17]	78 [12, 94]	<0.001
Feeding in RSL >75% of the time, %	N/A	0 (0)	21 (57)	<0.001
Supine Position Post-Prandial, %	N/A	50 [40, 66]	87 [74, 96]	<0.001
Supine Position Post-prandial >75% of the time, %	N/A	7/34 (21)	27/36 (75)	<0.001
Feeding Duration				
% time feed duration >30 min, %	N/A	4 [0, 37]	15 [0, 69]	0.15
Feeding Duration at Inception, min	N/A	23 [17, 41]	30 [19, 34]	0.64
Feeding Duration at Time 2, min	N/A	23 [18, 28]	26 [20, 30]	0.15
Long-term Follow-up†				
Feeding Method at 6 months – n (%)				0.65
PO	36/50 (72)	21/27 (78)	15/23 (65)	
Transition (PO + Tube)	10/50 (20)	4/27 (15)	6/23 (26)	
Tube	4/50 (8)	2/27 (7)	2/23 (9)	
Feeding Method at 1 year – n (%)				0.11
PO	37/44 (84)	20/22 (91)	17/22 (77)	
Transition (PO + Tube)	4/44 (9)	0/22 (0)	4/22 (18)	
Tube	3/44 (7)	2/22 (9)	1/22 (5)	
CCABSID-III				
Cognitive Score <80 – n (%)	9/44 (21)	5/23 (22)	4/21 (19)	1.00
Cognitive Score – #	95 [90 - 105]	100 [90 - 105]	90 [90 - 100]	0.11
Receptive Communication <80 – n (%)	14/42 (33)	8/23 (35)	6/19 (32)	0.83
Receptive Communication Score – #	90 [77 - 103]	91 [74 - 103]	89 [77 - 103]	0.75
Expressive Communication <80 – n (%)	11/25 (44)	7/14 (50)	4/11 (36)	0.69
Expressive Communication Score – #	88 [71 - 100]	81 [71 - 94]	89 [71 - 103]	0.66
Fine Motor <80 – n (%)	11/41 (27)	5/23 (22)	6/18 (33)	0.49
Fine Motor Score – #	94 [79 - 103]	97 [82 - 110]	88 [70 - 97]	0.13

[figure not shown]
Data presented as n (%), Median [IQR], or Mean (SD). \*1 value missing from both conventional and study groups. †Data was not available for all subjects for long-term follow up outcomes, n values are reported.

**Table 3. Feeding and I-GERQ-R Outcomes by Feeding Method at Inception**

Outcome	Conventional	Study	P-value
Among those Tube fed at Inception			
Achieved exclusive oral feeding	N = 18	N = 20	
Achieved I-GERQ-R decrease $\geq 6$	11 (61)	7 (35)	0.11
Achieved PO or I-GERQ-R decrease $\geq 6$	7/17 (41)	8 (40)	0.94
Achieved exclusive oral feeding + I-GERQ-R decrease $\geq 6$	14 (78)	13 (65)	0.39
	4/17 (24)	2 (10)	0.38
Among those PO fed at Inception	N = 17	N = 17	
Maintained PO	16 (94)	17 (100)	1.0
Achieved I-GERQ-R decrease $\geq 6$	4/14 (29)	5/14 (36)	1.0
Maintained PO or I-GERQ-R decrease $\geq 6$	16 (94)	17 (100)	1.0
Maintained PO + I-GERQ-R decrease $\geq 6$	4/14 (29)	5/14 (36)	1.0

[figure not shown]
Data presented as n (%).

**FIGURE 1.**

**Figure 1. Study Enrollment and Randomization.** Depicted is the CONSORT diagram describing participant flow and randomization into the conventional or study bundles, and subjects analyzed for outcomes.

## FIGURE 2

**Figure 2. I-GERQ-R Outcomes.** Depicted is a combination plot by group (boxplots) and individual I-GERQ-R scores (black line represents median). Note that parent perception scores (I-GERQ-R) significantly decreased in both groups at Time-2.

**Nationwide Children's Hospital IRB REVISION HISTORY**

Revision #	Version Date	Summary of Changes	Consent Change?
1	11/30/2012	Because NICU infants have lower fluid prescriptions in general, revised allowable total fluid volume from $\geq 170$ ml/kg/day to $\geq 150$ ml/kg/day at inception to be eligible for screening	No
2	2/15/2013	Because convalescing NICU infants with lung disease can have varying supplemental oxygen requirements, revised allowable respiratory support from Room air or $\leq 0.3$ LPM via nasal cannula to $\leq 1.0$ LPM or Room air at inception to be eligible for screening	No
3	12/9/2013	Because parents and providers did not permit stopping the PPI at 4 weeks for clinical reasons, allowed the subject to remain on medication at the follow up evaluation	No
4	3/24/2014	Allowed Practitioners to increase permissible study medication dose as clinically indicated	No
5	7/29/14	Added the use of swallowing motility measurements to the mechanistic study protocol	Yes
6	9/19/2014	Convalescing subjects with Neonatal Abstinence syndrome admitted to NICU have feeding difficulties masquerading as GERD symptoms.	No

		Changed inclusion criteria to permit these infants to be screened for eligibility into the study	
7	5/1/2015	To examine sucking, swallowing and motility measures, sucking-swallowing rhythms were measured for the mechanistic study protocol	Yes
8	1/12/2018	Added reciprocity with The Ohio State University and included biostatistician, [name] into the study staff	yes

